preferred brand of cigarettes or receive monetary reinforcement for cigarettes not smoked. Participants will be given funds at the beginning of the self-administration session and will lose a portion of the funds for each cigarette smoked. When participants smoke in this protocol, we will use the Clinical Research Support System (CReSS; Plowshare Technologies, Borgwaldt KC, Inc) to measure smoking topography. The reliability and acceptability of use of the portable CReSS device is well documented,^{88,94} and is recommended over direct observation. Topography data will include puff CO volume, puff duration, and inter-puff interval. Puff level data will be averaged to compute mean topography variables for each participant.

Baseline Assessments

- **Demographics.** Participants will be asked to provide standard demographic information (age, gender, race/ethnicity) as well as history of medical problems and current treatments.
- **Smoking History Questionnaire.** Smoking history and pattern will be assessed with a semi-structured interview with items targeting smoking frequency, age of smoking initiation, years of being a regular smoker, etc. The Timeline follow-back method will be used to establish degree of cigarette use in the last 30 days (a baseline predictor).
- **Fagerström Test for Cigarette Dependence (FTCD).** The FTCD is a six-item scale designed to assess gradations in cigarette dependence.⁹⁵ The FTCD will be used as a baseline covariate in the analyses.
- **Questionnaire of Smoking Urges-Brief (QSU-Brief).** The QSU-Brief measures urge to smoke and craving.^{96,97} The baseline and deprivation window Total Craving Scores will be used as predictors.
- **Executive Function – Behavioral Regulation.** Baseline levels of behavioral regulation will be assessed with the Behavioral Regulation Index from the from the SOBC assay, Behavioral Rating Inventory of Executive Function – Adults (BRIEF-A, <http://scienceofbehaviorchange.org/measures/>).
- **Psychological Distress.** Baseline levels of psychological distress will be assessed with the SOBC assay, Kessler Psychological Distress Scale (K6+, <http://scienceofbehaviorchange.org/measures/>).

Mechanistic Targets: The Triple-Risk Variables

Each of the mechanistic targets will be assessed at the post-intervention standard-smoking and deprivation-window assessments.

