- **Negative Affectivity/Stress:** Negative affect will be assessed with the SOBC assay, PANAS (PANAS-state negative (<http://scienceofbehaviorchange.org/measures/>), and withdrawal symptoms will be assessed with the Wisconsin Smoking Withdrawal Scale (WSWS).⁹⁸ Each of these mechanistic targets will be assessed at the standard smoking and deprivation-window assessments.
- **WM.** We focus on WM capacity as a mechanistic target due to its centrality to executive functions; its predictive validity across a wide range of health behavior applications, specifically including smoking; relevance as a modifiable treatment target; and interaction with negative affectivity/stress.¹ To provide multi-domain assessment of WM,^{99,100} we will adopt 3 specific SOBC assays : Adaptive N-Back, Digit Span, and Spatial Span (<http://scienceofbehaviorchange.org/measures/>). [name], *Study Consultant*, will aid the study team in quality control for these assessments.
- **Distress Tolerance.** We likewise focus on DT as a mechanistic target due to its predictive validity across a wide range of health behaviors (specifically including smoking); relevance as a modifiable treatment target; and amplification of negative affectivity/stress.¹ Because self-report and behavioral measures of DT are only partially correlated,³⁵ we will utilize both assessment strategies. For self-report we will use the ASI-3, an 18-item measure of AS.¹⁰¹ The ASI-3 has sound psychometric properties, including excellent internal consistency, predictive validity, and reliability among treatment-seeking smokers.¹⁰² Behavioral Distress Tolerance will be assessed with the computerized Mirror-Tracing Persistence Task (MTPT-C),¹⁰³ with evidence this measure captures the inability to tolerate distress and not just the experience of distress itself.¹⁰⁴ [name] and [name] will aid the study team in quality control for these assessments.

Interventions

All interventions are delivered in six, 90-minute individual sessions over 3 weeks. Sessions will be recorded for supervision/quality assurance review by [name].

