Engaging Working Memory and Distress Tolerance to Aid Smoking Cessation

NCT03565497

R21 DA046963

Updated: 8/5/2019

Analytic Plan

Note: Due to limited sample size the full analytic plan for this project could not be enacted validly.

Analyses for outliers, non-normal distributions, nonlinear relations, and influence statistics will be conducted; data transformations will be considered where appropriate. We will analyze data using mixed effects regression models (MRM) because they allow inclusion of all participants regardless of missing data (which improves power and generalizability) and are the recommended method for longitudinal data analysis (Hamer & Simpson, 2009). For each analysis, the distribution of the DVs will be evaluated and appropriate linking functions and outcome distributions will be used if the DVs are not normally distributed (in these cases the analysis will be generalized linear mixed models). For all analyses, the following baseline assessments will be included as covariates in the analyses: cigarette use in the last 30 days, FTCD score, QSU score, BRIEF-A scores for the Behavioral Regulation Index, and psychological distress from the K6+ symptoms.

Aim 1. We will perform repeated-measures MANCOVAs using MRMs. IVs will be intervention condition (3 levels) and assessment context (smoking vs. deprivation; 2 levels). One MANCOVA will be performed for each of the three risk categories (stress reactivity, WMC, DT) with the multiple measures of each risk factor being the multivariate DVs. For Aim 1a, we will use contrasts to test whether Mindfulness and Mindfulness+IE will each significantly improve stress reactivity, WMC, and DT relative to the control condition (CC), during the standard smoking assessment. For Aim 1b, we hypothesize that Mindfulness+IE will significantly improve stress reactivity, WMC, and DT relative to both the Mindfulness and CC conditions, during the smoking deprivation assessment.

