Exploratory Analyses: 1) In consideration of sex as a biological variable, sex and the interactions between sex and all predictors will be considered in exploratory analyses for each Aim. 2) We will examine whether ASI moderates the effects of treatment condition and context (stress) on the risk categories in Aim 1, by adding ASI and its interaction with the treatment condition and context to the MMRMs in Aim 1. 3) We will examine smoking topography as a predictor of outcomes in Aims 2 and 3. 4) We will examine number of intervention sessions attended and dropouts to aid data interpretation and future study planning.

Power Analysis. We used PinT 2.12 (Power in Two-Level models) to calculate the smallest effect size detectable given our N=75 at the deprivation assessment. Since no power analysis programs are available for multivariate MRM, we performed power analyses for the univariate MRMs knowing that power for the multivariate MRMs will be greater.¹⁰⁸ PinT indicated that we had greater than .80 power to detect an effect size of $d = .40$ for **Aim 1**, $d = .39$ for **Aim 2**, and $d = .48$ for **Aim 3**. As per research detailed above,^{54,63,64,71,82,109} there is preliminary evidence indicating that our interventions have the ability to activate mechanistic targets, and for mechanistic targets to be related to clinical outcomes, at effect sizes beyond these powered values.

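### The SAP claims more than .80 power at d = .40 for Aim 1, but the planned 25 v 25 contrasts have about 0.28 (0.50 if covariates explain half the variance) when d is a between-arm difference in SDs

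*SAP*

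**What the plan says.** The SAP's Power Analysis section used PinT "to calculate the smallest effect size detectable given our N=75 at the deprivation assessment" and reports for Aim 1: "PinT indicated that we had greater than .80 power to detect an effect size of $d = .40". The calculation was for univariate mixed models. The SAP adds, without a figure, that the multivariate models will have more power, and that preliminary evidence points to effects larger than the powered values.

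The tests are set out under Aim 1. For Aim 1a, in the standard smoking context, "we will use contrasts to test whether Mindfulness and Mindfulness+IE will each significantly improve stress reactivity, WMC, and DT" relative to control. For Aim 1b the hypothesis is that "Mindfulness+IE will significantly improve stress reactivity, WMC, and DT relative to both the Mindfulness and CC conditions, during the smoking deprivation assessment". All are pairwise arm comparisons within a single context.

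On adjustment, the Analytic Plan says: "For all analyses, the following baseline assessments will be included as covariates in the analyses". The five are 30-day cigarette use, FTCD, QSU, the BRIEF-A Behavioral Regulation Index and K6+. The Protocol, under Mechanistic Targets, says: "Each of the mechanistic targets will be assessed at the post-intervention standard-smoking and deprivation-window assessments". Neither the Protocol's Baseline Assessments list nor the covariate list includes a target measure used as an Aim 1 outcome.

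The SAP does not give alpha, sidedness, allocation, variance components, covariate R², the contrast powered, or what d is standardised by.

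**The concern.** Seventy-five participants in three arms leave about 25 per arm. A comparison of 25 with 25 normally has 80% power only for a difference near 0.8 SD, so .40 is about half what one would expect.

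Two things are at stake. First, a reader who takes d in its ordinary sense will believe that a null Aim 1 contrast is informative about effects of 0.40 SD. On that reading such an effect would be missed about 7 times in 10 unadjusted, 6 in 10 at R² = .3 and 5 in 10 at R² = .5. Second, the SAP checks its preliminary evidence against the stated thresholds. If the Aim 1 threshold is too low, that check is too easy to pass.

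**Working it through.** **Inputs from the documents.** 75 assessed (SAP, Power Analysis). Up to 107 randomised to reach that number, so 75 is already net of dropout (Protocol, Participant Selection). Three arms (Protocol, Design Overview). Pairwise within-context contrasts and five covariates (SAP, Analytic Plan).

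**Assumed, because not stated.** 1:1:1 allocation, two-sided alpha .05, covariate R² from 0 to .75, correlation between measures from .3 to .7.

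**1. Trying to reproduce .40.** For 25 v 25 the standard error multiplier is √(1/25 + 1/25) = 0.2828. The smallest difference with 80% power is (1.960 + 0.842) × 0.2828 = 0.792 SD by the normal formula, or 0.809 SD by noncentral t (df 48). Half of that is .396 to .404. So .40 is matched if it is a standardised slope or a ±1-coded arm effect, which means 0.79 to 0.81 SD between arms.

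Other scales also reach or nearly reach the stated power:
- Cohen's f = .40 in the three-arm omnibus test gives .869, but that f means 0.85 to 0.98 SD between extreme arms.
- A paired or one-sample d of .40 gives .79 with n = 50 and .93 with n = 75.
- A difference of differences gives .89 if the two contexts correlate at .9.

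None of these is a pairwise within-context contrast at 0.40 SD.

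**2. The planned contrast, with d a between-arm difference in SDs.** Noncentrality λ = d / [√(1 − R²) × 0.2828], with df = 75 − 3 − 5 = 67. The simulation column fits three arms of 25 with five random covariates (20,000 runs).

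| R² | λ at d = .40 | Power (formula) | Power (simulation) | Detectable d at 80% |
|---|---|---|---|---|
| 0 | 1.414 | .286 (.283 on df 48) | .278 | .804 (.809 on df 48) |
| .3 | 1.690 | .385 | .360 | .673 |
| .5 | 2.000 | .505 | .466 | .569 |
| .7 | 2.582 | .721 | – | .440 |
| .75 | 2.828 | about .80 | .769 | about .40 |

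**3. R² needed.** For 80% power λ must be .804 / 0.2828 = 2.843, so R² = 1 − (1.414 / 2.843)² = .752, a multiple correlation of √.752 = .87.

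**4. Sample size needed, unadjusted.** n per arm = 2 × (1.960 + 0.842)² / .40² = 98.1, so 99 per arm, or 297 assessed.

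**5. More generous assumptions at d = .40.**

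| Assumption | Power, R² = 0 | Power, R² = .5 |
|---|---|---|
| One-sided test | .401 | .631 |
| All 107 analysed (35 v 36) | .383 | .658 |
| Both active arms pooled v control (50 v 25) | .364 | .624 |
| Average of both contexts, correlation .5 | .37 | .64 |
| Both contexts counted as independent (50 v 50) | .508 | – |

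Averaging the contexts reaches about .81 only with zero correlation between them and R² = .5, and it is not the planned contrast.

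**6. Does the multivariate model close the gap?** Take d = .40 on each of k measures with correlation ρ = .3 / .5 / .7, two-sided.

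| Test | k = 2 | k = 3 |
|---|---|---|
| Omnibus Hotelling, R² = 0 | .311 / .274 / .245 | .312 / .254 / .216 |
| Common 1-df effect, R² = 0 | .405 / .360 / .324 | .475 / .397 / .341 |
| Common 1-df effect, R² = .5 | .686 / .624 / .571 | .770 / .675 / .596 |

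The omnibus test falls below the univariate one once ρ exceeds about .44 (k = 2) or .39 (k = 3). So multivariate power is not always greater. A common effect cannot be presumed for distress tolerance either: the Protocol notes that "self-report and behavioral measures of DT are only partially correlated".

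**7. Aim 2 has the same ambiguity.** As a mean-difference metric, d = .39 is r = .39 / √(.39² + 4) = .191, with power about .38 at N = 75. Read as a correlation of .39, power is about .94.

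**The case against.** The strongest reply is that no stated figure has been shown to be wrong. The SAP speaks of an effect size in a two-level model. It never says that .40 is a between-arm difference in SDs, nor that it refers to the Aim 1a and 1b contrasts, and some scales do give more than .80. Alpha, sidedness, allocation and R² in the check are assumptions. That stands, and it is why the finding is conditional and alleges no PinT fault. It does not rescue the statement: the alternatives are either not the planned contrast or amount to about 0.8 SD or more between arms.

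The Aim 1 hypotheses are directional, and a one-sided common effect over three measures at R² = .5 would have power of about .86 at ρ = .3 and .78 at ρ = .5. That is correct, so the multivariate figures above are not a ceiling. They hold for two-sided tests, and the Hotelling rows are unadjusted. But the SAP states its power for the univariate model, where one-sided testing still needs R² of about .68.

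Whether the preliminary effects exceed the true threshold cannot be judged from these documents. Only the threshold they are compared with is in question.

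Finally, the SAP opens by conceding that "Due to limited sample size the full analytic plan for this project could not be enacted validly". This warns the reader and lowers the consequence, but it neither corrects the power figure nor supplies the missing inputs.

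**Conclusion.** The concern holds. On the ordinary reading of d, the design does not deliver the stated power for its own Aim 1 contrasts: about 0.28 to 0.50 instead of more than .80, where the upper end requires covariates that explain half the outcome variance. The detectable difference is about 0.57 to 0.80 SD, not 0.40. On a slope or ±1 scale the number is attainable but means about 0.8 SD between arms, so the label misleads. The result rests on equal allocation, two-sided alpha .05 and 75 analysed. It does not hinge on any one of these: relaxing sidedness, sample size or pooling singly still leaves power at or below 0.66, even at R² = .5. An R² near .75 would rescue the figure, but no baseline value of a target measure is among the covariates. This should be fixed. It bears on how Aim 1 results are read and does not invalidate the design.

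**What to change.** First state what .40 refers to: the contrast, the scale, and the PinT variance components, R², alpha, sidedness and allocation. Do the same for d in Aims 2 and 3. Then restate Aim 1 for the planned contrasts, with the R² values marked as illustrative:

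> With N = 75 (about 25 per arm, equal allocation) and two-sided alpha .05, 80% power is available for a pairwise contrast within one context of about 0.80 SD unadjusted, 0.67 SD if the baseline covariates explain 30% of outcome variance, and 0.57 SD if they explain 50%.

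Replace the multivariate remark with:

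> Multivariate power may be higher or lower than univariate power, depending on the test and on the correlation between measures.

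Recheck the comparison with preliminary evidence against the restated figures, and soften it if needed.

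The cost is SAP wording and a less favourable stated threshold. No extra participants are needed, and neither the design nor the analysis changes.
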